- Systemic anti-vascular endothelial growth factor (VEGF) agents
- ITV anti-VEGF agents (other than ranibizumab) in either eye
- ITV, subtenon, or chronic topical (ocular) corticosteroids in the study eye
- Systemic or IV immunomodulatory therapy (e.g., azathioprine, methotrexate, mycophenolate mofetil, cyclosporine, cyclophosphamide, anti-tumor necrosis factor α agents)
- *Ocular or systemic* complement inhibitors, (e.g., eculizumab) except lampalizumab
- Treatment with Visudyne[®] in either eye
- Other experimental therapies (except *those involving* vitamin and mineral supplements)

Excluded Concomitant Conditions

Medical or surgical conditions or clinical laboratory findings giving reasonable suspicion of a disease or condition that contraindicates the use of an investigational drug, or that might affect interpretation of the study results, or that may render a study patient at high risk for treatment complications; when such a condition is identified, consultation with the Medical Monitor will be required to determine a patient's eligibility to continue in the extension study.

Statistical Methods

Safety Analysis

Safety will be assessed by adverse events, clinical laboratory evaluations, and immunogenicity as measured by ATA. Safety analyses will include all patients who enrolled into the extension study and received at least 1 lampalizumab injection in the extension study. These patients will be grouped by the treatment received (*lampalizumab or sham*) when they were enrolled in Study CFD4870g or Study GX29455 for safety analyses.

The primary safety analysis is planned to occur at the time when patients enrolled from Study CFD4870g have reached approximately 96 months follow up and when patients enrolled from Study GX29455 have reached approximately 54 months follow- up. The timing of the primary analysis may be adjusted according to the start of the open-label extension for Studies GX29176 and GX29185, to which patients from the extension study may have the opportunity to enroll. Earlier safety analyses of this study may be performed on an ad hoc basis.

All verbatim adverse event terms will be mapped to Medical Dictionary for Regulatory Activities (MedDRA) thesaurus terms, and adverse event severity will be graded according to an adverse event severity grading scale.

Missing Data

All efforts will be made to minimize missing data; no imputation will be performed for the safety analysis.

Determination of Sample Size

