2. OBJECTIVES

2.1 PRIMARY OBJECTIVE

The primary objective of this study is as follows:

- To investigate the long-term ocular and systemic safety and tolerability of lampalizumab administered ITV monthly

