3.4 OUTCOME MEASURES

3.4.1 Primary Outcome Measure

- *Nature, incidence, and severity of ocular and non-ocular adverse events*

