4.1.3.2 Concurrent Systemic Conditions

- Uncontrolled blood pressure (defined as systolic greater than 180 mmHg and/or diastolic greater than 110 mmHg while the patient is sitting)
- Medical conditions that may be associated with a clinically significant risk for bleeding
- Metabolic dysfunction, physical examination finding, or clinical laboratory finding giving reasonable suspicion of a disease or condition that contraindicates the use of an investigational drug or that might affect interpretation of the results of the study or that renders the patient at high risk for treatment complications
- Predisposition to increased risk for infection
- Active malignancy within the past 12 months except for appropriately treated carcinoma in situ of the cervix, non-melanoma skin carcinoma, and prostate cancer with a Gleason score of <6 and a stable prostate-specific antigen for > 12 months.
- Allergy to fluorescein, not amenable to treatment
- Inability to obtain study images of sufficient quality to be analyzed and graded by the central reading center
- Inability to comply with study or follow-up procedures
- Requirement for continuous use of any medications/treatments indicated in the “Excluded Concomitant Therapy” Section [4.5.2](#)

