4.5.3 Excluded Concomitant Conditions

- Medical or surgical conditions or clinical laboratory findings giving reasonable suspicion of a disease or condition that contraindicates the use of an investigational drug, or that might affect interpretation of the study results, or that may render a study patient at high risk for treatment complications; when such a condition is identified, consultation with the Medical Monitor will be required to determine a patient's eligibility to continue on the extension study

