4.8 STUDY TREATMENT DISCONTINUATION

The investigator has the right to discontinue a patient from the study treatment for any medical condition that the investigator determines may jeopardize the patient's safety if he or she continues in the study treatment, for reasons of non-compliance (e.g., missed doses, visits), if the patient becomes pregnant, or if the investigator determines it is in the best interest of the patient. The reason for the treatment discontinuation should be recorded on the appropriate eCRF.

Treatment discontinued patients will be also discontinued from the study and will not be replaced or allowed to re-enter the study.

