5.1.1 Adverse Events

According to the ICH guideline for Good Clinical Practice, an adverse event is any untoward medical occurrence in a clinical investigation subject administered a pharmaceutical product, regardless of causal attribution. An adverse event can therefore be any of the following:

- Any unfavorable and unintended sign (including an abnormal laboratory finding), symptom, or disease temporally associated with the use of a medicinal product, whether or not considered related to the medicinal product
- Any new disease or exacerbation of an existing disease (a worsening in the character, frequency, or severity of a known condition), except as described in Section 5.3.5.9
- Recurrence of an intermittent medical condition (e.g., headache) not present at baseline
- Any deterioration in a laboratory value or other clinical test (e.g., ECG, X-ray) that is associated with symptoms or leads to a change in study treatment or concomitant treatment or discontinuation from study drug
- Adverse events that are related to a protocol-mandated intervention, including those that occur prior to assignment of study treatment (e.g., screening invasive procedures such as biopsies)

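### A post-enrolment condition that only complicates interpretation can put continued participation in question, although in this safety study it is outcome data, so later follow-up may be cut short because of the outcome

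*Combined protocol and SAP*

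**What the plan says.** The synopsis (Excluded Concomitant Conditions) and Section 4.5.3 cover medical or surgical conditions and laboratory findings that raise reasonable suspicion of one of three things. One is a contraindication to an investigational drug. The other two are in the words "or that might affect interpretation of the study results, or that may render a study patient at high risk for treatment complications". In that case, "consultation with the Medical Monitor will be required to determine a patient's eligibility to continue in the extension study"; Section 4.5.3 has the same operative text.

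Section 4.1.3.2 uses nearly the same wording as an entry exclusion: a finding that suggests a condition that "contraindicates the use of an investigational drug or that might affect interpretation of the results of the study".

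The primary objective (Section 2.1) is "To investigate the long-term ocular and systemic safety and tolerability of lampalizumab administered ITV monthly". The primary outcome (Section 3.4.1) is "Nature, incidence, and severity of ocular and non-ocular adverse events". Section 5.1.1 counts as an adverse event "Any new disease or exacerbation of an existing disease (a worsening in the character, frequency, or severity of a known condition"; the stated exception is the expected progression of geographic atrophy (Section 5.3.5.9).

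Section 4.8 makes leaving treatment final: "Treatment discontinued patients will be also discontinued from the study and will not be replaced or allowed to re-enter the study". Section 5.3.1 ends adverse event reporting at the last study visit. For a patient who leaves early, that is an early termination visit at least 30 days after the last dose (Section 4.6.4).

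**The concern.** At entry, excluding a patient whose illness would muddy the results is ordinary practice, because baseline illness is not outcome data. After Day 1 the same illness is what the study exists to record. Section 3.5 names the systemic effects being looked for: cardiovascular disease, cancers and changes in immune function. Any of these could be said to affect interpretation.

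If a patient leaves on that ground, follow-up stops because of the outcome. Patients who have just developed a disease may well be those at higher risk of further events, and planned follow-up is about 96 months (patients from CFD4870g) or 54 months (patients from GX29455). An early departure could therefore cost years of observation. The study has no control group (Section 3.7) to reveal or offset a distortion. The events most exposed are later ones that an investigator would not call related. In an uncontrolled study, aggregate rates of such events are the main check on those individual judgements.

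**Working it through.** **Reading the passages together**

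1. *Time of application.* The clause asks about eligibility to continue, so it operates during follow-up. It does not define what affects interpretation and does not exempt adverse events.
2. *Overlap with the outcome.* Under Section 5.1.1 a new disease is an adverse event. Not every laboratory abnormality is (Section 5.3.5.4), but laboratory evaluations are part of the safety analysis (Section 4.12.1). The same finding can be a study result and a reason to review continuation.
3. *What this ground adds.* Contraindication and high risk are separate grounds in the same clause. Section 4.7 also allows withdrawal for a condition that endangers the patient. The interpretation ground matters only where none of these applies.
4. *What is kept.* The triggering event is recorded up to the last visit (5.3.1). Every patient with at least one extension injection stays in the safety population (4.12.1). Known events are followed to resolution or stability (5.4.1), and related ones even after participation ends (Appendix 1 schedule footnotes). Later serious events believed related are reportable (5.5).
5. *What can be lost.* New events after the last visit that are not serious, or not believed related.
6. *Analysis.* No imputation is planned (4.12.4). Section 4.12 describes no exposure-adjusted rate and no sensitivity analysis for such withdrawals.

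**Direction of the effect**

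The plan states no figure to reproduce. The calculation below shows direction only. Follow-up T comes from the protocol (96/12 = 8.0 years; 54/12 = 4.5 years). All other inputs are assumptions:

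- a = 0.05 per year, the hazard of a first later event before the condition
- k = 1 to 3, the multiple of that hazard afterwards
- c = 2% to 10% per year, onset of a qualifying condition
- f = 0%, 50% or 100% of affected patients leaving one month after onset

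With H the share event-free without the condition and D the share event-free with it and still followed: dH/dt = -(a + c)H; dD/dt = cH - kaD - departures. The triggering condition is not counted as a later event.

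Hand check with c = 0.05, k = 2, T = 8 and no departures: H = exp(-0.1t) and D = 0.05t·exp(-0.1t). The share with an event is 1 - exp(-0.8) × 1.4 = 37.1%. Person-years per patient are 5.51 + 0.96 = 6.46. The rate is 37.1/6.46 = 5.74 per 100 patient-years.

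| T (years) | c | k | Rate per 100 patient-years: none / half / all leave | Share of all treated with a later event, %: none / half / all leave |
|---|---|---|---|---|
| 8.0 | 2% | 2 | 5.32 / 5.17 / 5.01 | 34.8 / 32.7 / 30.7 |
| 8.0 | 5% | 1 | 5.00 / 5.00 / 5.00 | 33.0 / 30.3 / 27.6 |
| 8.0 | 5% | 2 | 5.74 / 5.41 / 5.02 | 37.1 / 32.4 / 27.8 |
| 8.0 | 10% | 3 | 7.43 / 6.42 / 5.08 | 45.8 / 34.8 / 23.9 |
| 4.5 | 2% | 2 | 5.20 / 5.10 / 5.01 | 20.9 / 20.1 / 19.4 |
| 4.5 | 10% | 3 | 6.67 / 5.94 / 5.08 | 26.2 / 21.5 / 16.8 |

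The crude share falls in every row. The rate falls only when k exceeds 1, and would move the other way if k were below 1. The all-leave column is an extreme: in the 8-year, 5%, k = 2 row it means 27.1% of patients leaving on this ground.

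**The case against.** The strongest reply is that the clause orders nothing: "consultation with the Medical Monitor will be required to determine a patient's eligibility to continue on the extension study" is a requirement to consult. A reader might infer that the Medical Monitor alone can end participation, or that a qualifying condition leads to removal. The text supports neither; it does not name who decides and leaves the result open.

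The protocol also keeps many patients with foreseeable conditions. Choroidal neovascularization, glaucoma and cataract may be treated on study, and Table 2 turns many ocular events into dose holds with possible resumption. What remains is mainly systemic disease, and nothing in the documents shows that the clause was ever used for it.

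Other routes truncate follow-up in the same way: the contraindication and high-risk grounds, the Table 2 discontinuations, and the non-exhaustive list in Section 4.7. Changing one phrase does not remove them. The phrase may also protect the geographic atrophy and visual acuity summaries.

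Most of this stands and limits the point. It does not dispose of it. The interpretation ground is the one part of the clause with no stated patient-safety purpose. The imaging and acuity summaries fall under exploratory analyses (Section 4.12.3), and affected data can be flagged there without ending collection of the primary outcome.

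**Conclusion.** The concern holds in a limited form. The synopsis and Section 4.5.3 permit, but do not require, outcome-dependent loss of later follow-up on a data-quality ground. The likely bias is toward fewer later events, chiefly those not judged related. For crude incidence that direction needs only that some later events go uncollected; for a person-time rate it also needs a raised event rate after the condition.

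A reader might infer that the triggering event disappears from the analysis. It does not, and a patient-level proportion with any adverse event already counts that patient. A reader might also take a percentage understatement from the illustration. The documents give no onset rate, no later-event rate and no frequency of removal, so the size is unknown and may be small. The point is worth correcting because the correction is cheap, not because a large bias has been shown.

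**What to change.** Reconcile the synopsis and Section 4.5.3 with Sections 3.4.1 and 5.1.1 so that interpretability alone is not a ground for ending collection of safety data after Day 1. The entry criterion in Section 4.1.3.2 is not affected. The contraindication and high-risk grounds, and every decision about treatment, remain with the sponsor. Because Section 4.8 ties leaving treatment to leaving the study, the sponsor also needs to state how continued safety data collection fits with that section and with Section 4.7.

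Sections 4.7 and 4.8 already require a reason on the case report form. Add a separate code for the interpretation ground, list each such withdrawal with its triggering event in the safety report, and continue safety data collection to the planned end where consent allows.

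The cost is a wording change in two places with matching text in Sections 4.7 and 4.8, one reason code, one listing, and continued contact with the patients concerned. The downside is that some patients with confounding illness remain in the geographic atrophy and visual acuity summaries, where they can be flagged.

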1.2 BACKGROUND ON THE MOLECULE

Lampalizumab is an antigen-binding fragment (Fab) of a humanized monoclonal antibody directed against the complement component factor D (CFD). Lampalizumab binds human factor D with a dissociation equilibrium constant of approximately 20 pM. Factor D is a highly specific serine protease that is a rate-limiting enzyme of the ACP. The substrate for factor D is another alternative pathway serine protease, complement factor B (CFB). Following cleavage by CFD, CFB converts into the proteolytically active complement factor Bb and initiates the ACP. Lampalizumab inhibits ACP activity by preventing CFD-mediated cleavage of CFB. Lampalizumab activity is specific for the ACP and shows no inhibitory effect on the classical or mannose-binding lectin complement pathways.

Through inhibition of ACP activity, lampalizumab may offer the potential to impede or arrest the progression of GA and visual function loss. Evidence for CFD in the pathogenesis of AMD includes protection against oxidative stress-mediated photoreceptor degeneration in a murine model with genetic deficiency of CFD ([Rohrer et al. 2007](#)) and detection of increased systemic activation of complement components, including CFD, in the serum of patients with AMD versus controls, which suggests that AMD may be a systemic disease with local manifestations in the aging macula ([Scholl et al. 2008](#)).

See the lampalizumab Investigator's Brochure for additional details on nonclinical and clinical studies.

1.3 RATIONALE FOR DOING THIS STUDY

The open-label extension study will provide data to investigate the long-term safety and tolerability of lampalizumab in patients with GA. At present, there is no approved treatment to prevent the progression of GA and vision loss; lampalizumab is being studied as a potential treatment for this indication. For patients who complete the 18-month treatment assignment in Study CFD4870g or 24-week treatment assignment in Study GX29455, Study GX28198 will permit the evaluation of long-term safety and tolerability of lampalizumab in participants continuing from the active treatment arms. In addition, Study GX28198 will provide the opportunity for eligible patients from the sham treatment arms in Study CFD4870g or Study GX29455 to receive lampalizumab.

2. OBJECTIVES

2.1 PRIMARY OBJECTIVE

The primary objective of this study is as follows:

- To investigate the long-term ocular and systemic safety and tolerability of lampalizumab administered ITV monthly

2.2 EXPLORATORY OBJECTIVES

The exploratory objectives of this study are as follows:

- To assess long-term GA area progression with fundus autofluorescence (FAF), color fundus photographs (CFP), and spectral domain-optical coherence tomography (SD-OCT)
- To evaluate potential anatomic biomarkers for earlier-stage GA progression and pharmacodynamic outcomes (e.g., retinal substructure analysis by SD-OCT)
- To assess the incidence of anti-therapeutic antibodies (ATA) to lampalizumab
- Clinical genotyping to assess relationships between genetic polymorphisms associated with AMD, disease characteristics, and response to administration of lampalizumab

3. STUDY DESIGN

3.1 DESCRIPTION OF THE STUDY

Study GX28198 is a multicenter, open-label extension study of safety and tolerability of lampalizumab administered by ITV injection to patients with GA who have completed the 18-month treatment in Study CFD4870g or 24-week treatment in Study GX29455. As such, Study GX28198 is considered the extension for patients enrolled in these studies and is referred to as the extension study throughout the remainder of this protocol. CFD4870g patients who discontinued from study treatment early but remained in the study for safety evaluation, or discontinued prior to completion of the 18-month treatment period, were not eligible for Study GX28198. Patients who participated in Study GX29455 and discontinued from study treatment prior to completion of the 24-week treatment period are not eligible for the extension study. Site investigators will be ophthalmologists with subspecialty expertise in vitreoretinal diseases.

3.1.1 Patients Enrolled from Study CFD4870g

The extension study enrolled 2 groups of patients from Study CFD4870g: patients previously exposed to lampalizumab and patients who were lampalizumab-naïve (i.e., received sham treatment). Eligible patients who consented to participate in the extension study were enrolled at the conclusion of the Month 18 visit for Study CFD4870g; the Month 18 visit served as the final visit for Study CFD4870g and the Day 1 visit for the extension study. Upon enrollment, all patients received 10-mg ITV injections of lampalizumab. Initially, patients continued on the same dosing frequency (monthly or every-other month) assigned previously during their participation in Study CFD4870g. Patients in the every-other-month treatment arm were later crossed over to the monthly treatment arm for the remainder of their study participation period (see Section 3.3).

3.1.2 Patients Enrolled from Study GX29455

The extension study will enroll 2 groups of patients from Study GX29455: patients previously exposed to lampalizumab and patients who were lampalizumab-naïve (i.e., received sham). Eligible patients who consent to participate in the extension study will be enrolled at their conclusion of Study GX29455 (i.e., the Week 24 visit); the Week 24 visit will serve as the final visit for Study GX29455 and the Day 1 visit for the extension study.

All patients from Study GX29455 who enroll in the extension study will receive 10-mg ITV administrations of lampalizumab. The dosing frequency for both treatment arms (every 2 weeks [Q2W] and every 4 weeks [Q4W]) of Study GX29455 will change to monthly dosing to align with dosing in the extension study.

3.1.3 All Extension Study Patients

A patient must satisfy all eligibility criteria at Day 1 visit and will be enrolled using an interactive response system (IxRS). All patients enrolled in the extension study will have the first ITV injection of lampalizumab administered by the investigator at the Day 1 visit (unless dose holding is medically justified by the investigator) which is scheduled on the same day and immediately following the conclusion of the Month 18 visit for Study CFD4870g or Week 24 visit for Study GX29455. Requisite Study CFD4870g Month 18 and Study GX29455 Week 24 assessment data will be extracted and incorporated into extension study Day 1 datasets.

All patients who enroll in Study GX28198 will have scheduled monthly visits with monthly study-drug treatment for the duration of their study participation (see [Table 1](#)).

Table 1 Dosing Schema

Treatment	Day 1 ^a	Monthly Lampalizumab Dosing Visit Month 1 through Visit Month 95 ^b or Visit Month 1 through Visit Month 53 ^c	ET ^e or Final visit Month 96 ^d or Month 54 ^d
Lampalizumab 10-mg ITV injections	x	x	

ET = early termination; ITV =intravitreal.

- ^a Day 1 visit will occur at the conclusion of the Month 18 visit for Study CFD4870g or Week 24 visit for Study GX29455; the first study drug administration for the extension study is at the Day 1 visit.
- ^b Patients enrolled from Study CFD4870g in the monthly treatment arm continue to receive monthly lampalizumab treatment (Months 1–95) without change; patients in the every-other-month treatment arm were crossed over to the monthly treatment arm and are receiving monthly lampalizumab treatment for the remainder of their 95-month study treatment period.
- ^c Patients enrolled from Study GX29455 will receive monthly treatment (visit Months 1–53) with lampalizumab irrespective of the treatment arm (Q2W or Q4W) they were randomized to in Study GX29455.
- ^d Month 96 visit is a final study visit for patients enrolled from Study CFD4870g and Month 54 visit is the final study visit for patients enrolled from Study GX29455; no study treatment will be administered at the final visit.
- ^e *Patients may undergo an ET visit as per protocol section 4.7 through 4.9; no study treatment will be administered at this visit.*

At the scheduled monthly visits, patients will have safety assessments evaluated by the investigator prior to receiving study drug injection. Patients will be contacted by site personnel 7 (± 2) days after each injection to elicit reports of decrease in vision, eye pain, unusual redness, or any other new ocular symptoms in the study eye. *If warranted, patients will be asked to return to the clinic as soon as possible for an unscheduled safety assessment visit (see Appendix 1-F). Patients will be instructed to contact the investigator at any time if they have any health-related concern.* Patient self-administered antimicrobials in the pre- and post-injection period may be used at the investigator's discretion.

The study eye for the extension study will be the same eye that received lampalizumab or sham administrations in Study CFD4870g or in Study GX29455. Only the study eye will receive administration of lampalizumab in the extension.

The extension study is being extended by an additional 30 months to a total duration of 96 months *to provide study patients with access to treatment until potential commercialization of lampalizumab.* The monthly treatment arm patients enrolled from Study CFD4870g may receive up to 96 monthly ITV injections of study drug. The number of ITV injections of study drug for patients who enrolled from the every-other-month treatment arm will vary due to their later crossover to the monthly

treatment arm, which was relative to their Day 1 visit date. The patients who enroll from study GX29455 may receive up to 54 monthly ITV injections of study drug.

All monthly visits will occur relative to the patient's Day 1 visit date. Dosing should not occur earlier than 23 days after the previous dosing. Missed study drug doses will be made up *only in the following circumstance*:

- *If, during scheduled visit, a site encounters an unexpected issue (e.g., the IxRS is not able to assign the study kit, or other patient care issues), the patient's study treatment may be administered within 3 working days of that visit. The following assessments will be repeated on the day of the delayed study treatment: slit lamp examination, indirect ophthalmoscopy, and pre-treatment intraocular pressure (IOP) measurements. These assessments are to be recorded on the scheduled visit electronic Case Report Form [eCRF] and dated with the actual administration date.*

After the Day 1 visit, if a patient misses a study visit when ocular images are to be obtained (see [Appendix 1-A](#) through [Appendix 1-E](#)), the images must be obtained at the next scheduled visit that the patient attends.

Patients are expected to attend their scheduled visits unless there are extenuating circumstances justifying their inability to come to the clinic.

Patients who are prematurely discontinued from the study treatment in the extension study (prior to the Month 96 visit for patients enrolled from Study CFD4870g or prior to the Month 54 visit for patients enrolled from Study GX29455) will be also discontinued from the extension study and will be asked to return for an early termination (ET) visit ≥ 30 days following their last study drug treatment for monitoring of adverse events and the ET visit assessments ([Appendix 1-A](#) through [Appendix 1-E](#)).

Patients will remain masked to their treatment assignment in Study CFD4870g or Study GX29455, and investigators are not permitted to provide treatment assignment in Study CFD4870g or Study GX29455 until permitted by the Sponsor. The extension study is being conducted in the United States and Germany.

The VA examiner role will remain masked to the patients' study eye assignment.

